Celecoxib is a COX-2 selective non-steroidal anti-inflammatory drug (NSAID). It is used to treat osteoarthritis, rheumatoid arthritis, ankylosing spondylitis, and several other inflammatory conditions. It has been in clinical use in the USA for 16 years. Celecoxib is generally well tolerated, with mild to moderate upper GI complaints being the most common adverse event (McCormack 2011). Although celecoxib has been associated with an increased risk of cardiovascular events, including myocardial infarction (MI) and stroke, this has been inconsistent in meta-analyses (McCormack 2011). Nonetheless, due to this potential risk, LAM patients with a history of MI or stroke will not be entered on this trial. Celecoxib and other NSAIDs may increase risk of serious gastrointestinal (GI) ulceration, bleeding, and perforation. To minimize this risk, LAM subjects on this protocol will not take any other NSAID, and omeprazole will be permitted for use concurrently for any LAM subjects on this trial. In addition, LAM patients with a prior history of ulcer disease or GI bleeding will be excluded from this protocol. Celecoxib and other non-steroidal anti-inflammatory drugs (NSAIDs) are known to reversibly affect renal function. For this reason, subjects with impairment of renal function will be excluded from the trial, and renal function will be monitored among subjects on this trial.

c- Rationale and hypothesis

As shown above, we have demonstrated that COX-2 and prostacyclin synthase expression is markedly increased in TSC2 deficient cells, and have also shown that prostaglandin metabolites are altered in angiomyolipoma cells. We have shown that treatment with a COX-2 inhibitor changes the PG metabolite profile of the angiomyolipoma cells, and inhibits their growth in vitro. Furthermore we have shown that COX-2 inhibition reduces growth of TSC2 deficient cells in vivo in two *Tsc* mouse models. Thus, **we hypothesize that COX-2 inhibition may be effective for TSC and LAM patients in reducing LAM and angiomyolipoma cell growth, and in stabilizing lung function.**

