a- Inclusion and exclusion criteria

We will perform a two-center phase I trial of celecoxib (COX-2 inhibitor) administered at 200mg by mouth daily for 6 months. The two centers are BWH and the National Institutes of Health Clinical Center. Up to 12 adult women with LAM will be recruited at both sites, and up to 8 subjects at BWH (between 4-8 at each site). The study will use the following eligibility criteria.

Inclusion criteria

- a. Female of age 18 to 69
- b. Ability to give informed consent
- c. Definite diagnosis of LAM

Typical cystic change on CT scan of the chest plus one of the following i) biopsy or cytology of any tissue demonstrating LAM, ii) angiomyolipoma, chylothorax, clinical or genetic diagnosis of tuberous sclerosis, iii) serum VEGF-D > 800pg/ml

- d. post-bronchodilator forced expiratory volume in one second \geq 70% of predicted and DLCO \geq 70% predicted during baseline visit.
- e. Women of childbearing potential must agree to use two forms of barrier contraception after screening visit, for the duration of study participation and for 30 days after last dose.

Exclusion criteria

- a. History of intolerance to non-steroidal anti-inflammatory drugs (NSAIDs)
- b. History of current regular use (daily most days of the week) of NSAIDs
- c. History of use of rapamycin or everolimus
- d. Uncontrolled intercurrent illness
- e. Pregnant, breast feeding or planning to become pregnant in the next 2 years
- f. Significant hematological (platelet count <100.000/ μ l or hepatic abnormalities (Liver function tests >2 times normal).
- g. Use of an investigational drug within 30 days of study start
- h. Inability to attend scheduled clinic visits
- i. Inability to give informed consent
- j. Inability to perform spirometry
- k. Creatinine > 1.0 mg/dl or eGFR < 60 ml/min
- l. Pneumothorax within past 8 weeks
- m. History of malignancy in the last 2 years other than basal cell skin cancer
- n. Use of estrogen containing medication within 30 days of enrolment
- o. Currently taking doxycycline, metformin, lupron or simvastatin

- p. Unable to undergo MRI
- q. History of seizure within the last year
- r. History of hepatitis or known active hepatitis B or C, or HIV positive serology
- s. Angiomyolipoma of diameter ≥ 4 cm
- t. History of vascular disease, including myocardial infarction or stroke
- u. History of ulcers or GI bleeding
- v. Allergy to sulfonamides, unless subject has previously used Celecoxib without any adverse reactions.

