- i- VEGF-D analysis will be performed in [name] laboratory at BWH
- ii- Next generation sequencing (NGS) assay to detect TSC2 mutant LAM cells in FACS sorted circulating LAM cells and/or TSC2 mutations in plasma cell-free DNA will be performed at BWH in [name] laboratory

Transfer of specimens between sites will be necessary to complete the investigational analyses. Samples will be shipped overnight on dry ice Monday to Thursday to keep specimens frozen. Transferring site will keep a log of all specimens transferred. The receiving site will keep a log of when samples are received and analyzed.

Primary outcome measurements

We will perform a two-center phase I trial of celecoxib (COX-2 inhibitor) administered at 200mg by mouth daily for 6 months. A study investigator will obtain informed consent after detailed review of the consent form with potential study participants. Consenting subjects will be screened at the initial visit based on predefined inclusion/exclusion criteria. Subjects must have mild to moderate LAM (defined as definite LAM not requiring rapalog therapy), have no history of chronic non-steroidal anti-inflammatory drug use, have no previous history of treatment with rapamycin or everolimus, and have no angiomyolipoma of diameter > 4 cm. Enrolled subjects will receive celecoxib at an initial dose of 200 mg orally daily, with a single dose adjustment to 100mg PO QD permitted if needed.

Any subject who receives at least one dose of celecoxib will be included in the analysis for side effects. Dose limiting toxicity will be graded according to the National Cancer Institute's CTCAE v3.0 (http://ctep.cancer.gov/protocoldevelopment/electronic_applications/docs/ctcaev3.pdf). During the 6 months of the trial, there will be 3 study related visits. Clinical and laboratory evaluation is described below.

Since this dose of celecoxib (200mg PO QD) is routinely well tolerated in the clinical setting in patients with arthritis and other inflammatory disorders, we expect that it will be well-tolerated in LAM patients. However, we will carefully monitor GI tolerance and renal function, since celecoxib can lead to reversible renal impairment.

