We will perform assessments of clinical, functional and subject self-reported outcomes to assess potential benefit of celecoxib. Since lung function decline is a hallmark of LAM, we will perform spirometry, which will be interpreted in accordance with standard guidelines (Anonymous 1991). We will utilize the St. George's Respiratory Questionnaire (SGRQ) (Barr et al. 2000), as an assessment of the impact of treatment on dyspnea levels. Finally, we will record the incidence of hospitalization, complications from the disease, and other medical problems occurring during the study period

Stopping rules

The study will be monitored for the occurrence of a specified set of treatment related serious adverse events (TRSAE). The following two types of TRSAEs will be considered for early stopping of the study:

- Death considered to be probably or definitely related to Celecoxib

- Any grade IV toxicity considered to be probably or definitely related to Celecoxib

Subjects will be followed for 24 weeks while on therapy. During the 24 weeks of the trial, there will 4 study visits (screening visit and 3 visits while on therapy). Clinical and laboratory evaluations will be performed as outlined in Table 1.

Secondary outcome measurements

We will be performing several correlative studies as part of this protocol.

- a. VEGF-D levels. VEGF-D is well-known as a biomarker of LAM, and disease extent correlates with VEGF-D levels. Therefore we will measure VEGF-D prior to treatment and at serial time points during treatment. As this is a pilot study, formal statistical analysis is not planned.
- b. Circulating LAM cells. Circulating LAM cells may be isolated from peripheral blood of subjects on this trial, using density gradient and FACS methods. TSC2 mutations will be identified in these cells, if possible, and then the prevalence of LAM cells will be measured serially over time in subjects on this study. If no TSC2 mutation is identified, then mutations in other genes in this pathway (RHEB, MTOR) will be sought. However, we will not scan the entire genome in these analyses, but rather focus on just a few genes. We will test the number of circulating LAM cells over time to help assess whether the treatment, celecoxib, reduces the number of LAM cells.

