- c. Plasma biomarker analyses. Prostaglandin metabolites (PGE2 and 6-keto-PGF1-alpha), matrix metalloproteinases MMP2 and MMP9, cathepsin K, and a cytokine array will be measured on serial plasma samples (weeks 0, 8, 16, 24) from subjects on this trial. Marked changes in these metabolites are expected when subjects are on celecoxib, and this will serve as a potential biomarker of drug effect and compliance.
- d. Exhaled breath condensates (EBCs). EBCs will be obtained from subjects on this trial at the time of pulmonary function testing (week 0, 24). Subjects will be required to withhold food and carbonated beverages for one hour prior to EBC collection. An Rtube (Respiratory Research, Austin, TX) will be used to collect EBCs by tidal breathing through the mouth for 10 minutes without a nose clip. The metal sleeve surrounding the collection chamber will be chilled to -20°C for at least one hour prior to EBC collection. The EBC will then be stored at -80°C under N2 gas to prevent non-enzymatic oxidation of the parent fatty acids and lipid mediators. Samples will be analyzed for prostaglandin metabolites (PGE2 and 6-keto-PGF1-alpha).
- e. Plasma cell-free DNA (cfDNA) will be isolated from each subject on this trial at each time point a sample is drawn. The plasma will be separated, and cfDNA isolated. The cfDNA will be subject to targeted next generation sequencing to search for mutations in TSC2.

VI- Biostatistical analysis

b- Data variables

We will collect information about the safety of Celecoxib in women with LAM and TSC. In particular, we will collect data on the incidence of adverse events and severe adverse events. In addition, we will collect information about lung function at the screening visit and at the end of the study period. If subject has a renal angiomyolipoma at the screening visit, we will collect information about angiomyolipoma size at the end of the 6 months of therapy.

c- Statistical Methods

Sample Size Considerations

Common adverse event rate with Celecoxib provided in the package insert are between 0.2% and 6.0%. The below table gives the probability of seeing at least one case of common adverse event associated with Celecoxib, using different event rates (Table 2).

Table 2. Probability of observing at least one case of an adverse event

	Adverse event rate		
Sample size	6%	2.5%	0.2%
12	52%	26%	2.3%

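### With one arm, lung function tested only at entry and week 24, and no reference rate of decline, a change near zero cannot be told apart from slow untreated disease.

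*Combined protocol and SAP*

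**What the plan says.** All references are to the combined protocol and SAP.

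- **Hypothesis and aim.** Section I-c hypothesises that COX-2 inhibition may help in reducing cell growth "and in stabilizing lung function". Aim 1 (section II) asks whether celecoxib is safe and shows clinical benefit. Efficacy is to be examined in a pilot manner, with formal evaluation left to later phase II/III studies.
- **Entry.** Section III-a sets a floor of 70% of predicted for "post-bronchodilator forced expiratory volume in one second", and for DLCO ("70% predicted during baseline visit"). It excludes any "History of use of rapamycin or everolimus". Section V, Primary outcome measurements, adds: "Subjects must have mild to moderate LAM (defined as definite LAM not requiring rapalog therapy". No criterion concerns how fast lung function was falling.
- **Measurement.** Section V explains the choice of endpoint: "Since lung function decline is a hallmark of LAM, we will perform spirometry". Section VI-b says "we will collect information about lung function at the screening visit and at the end of the study period". Table 1 places full pulmonary function tests at baseline and at the week 24 or early termination visit. Section V, Secondary outcome measurements, agrees: breath condensate is taken "at the time of pulmonary function testing (week 0, 24").
- **Analysis.** Section VI-c compares baseline with 24 weeks for FEV1, FVC and DLCO by Wilcoxon signed-rank test, two-sided 0.05.

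No control arm, run-in, use of earlier tests, external comparator or expected rate of decline is given. Nor is there a statement of which lung-function result would count as benefit.

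**The concern.** The hoped-for effect on lung function is that nothing happens. In a test of change against zero, that is the null hypothesis. A null result here has three explanations that the design cannot separate: the drug arrested a decline, there was little decline to arrest, or 12 women over 24 weeks were too few to show one.

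The protocol's own background shows what is missing. It reports that rapamycin stabilised lung function in a randomised controlled trial and that function declined once the drug was withdrawn. Stability could be interpreted there because a control group and an off-drug course existed. This trial has neither: it has no comparison group, and the drug stops after Visit 4, the last scheduled visit.

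At stake is the lung-function part of the clinical-benefit question. Success of the pilot is meant to enable phase II/III work, and apparent stability could be carried forward as a signal although it may have been present before treatment.

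**Working it through.** **1. The plan's own figure.** The only sample-size calculation is Table 2, the probability of at least one adverse event in 12 women, 1 − (1 − p)^12. For p = 6%, 2.5% and 0.2% this gives 52.4%, 26.2% and 2.37%. The plan states 52%, 26% and 2.3%, so the table is reproduced apart from rounding in the last entry. No calculation exists for lung function, so everything below rests on assumed rates and SDs.

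**2. Expected untreated change.** Follow-up is 24/52 = 0.4615 year. Change = rate × 0.4615.

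| Assumed untreated FEV1 decline (mL/year) | Change over 24 weeks (mL) |
|---|---|
| 0 | 0 |
| 25 | −12 |
| 50 | −23 |
| 100 | −46 |
| 150 | −69 |

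**3. Precision of the 24-week change.** With within-woman SD s per test, SE of the mean change = √2 × s / √12. For s = 60, 100 and 150 mL (assumed) this is 24, 41 and 61 mL. Arrested decline and slow decline overlap.

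**4. What untreated women would show.** Take 12 completers, the exact two-sided Wilcoxon test (reject if the smaller rank sum is 13 or less, attained alpha 0.0425) and normally distributed changes. For an assumed decline of 30 to 120 mL/year (14 to 55 mL over 24 weeks) and an assumed SD of the change of 100 to 200 mL, simulated power is about 5% to 38%. A group given no drug would thus show no significant change in about 62% to 95% of trials. The 95% CI half-width is 0.635 × SD, or about 64 to 127 mL, wider than the whole assumed decline.

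**5. What a pre-treatment slope adds.** Take s = 100 mL, with earlier tests at −2 and −1 years and the screening test at 0. The prior slope is (y0 − y−2)/2. The paired difference is (y24 − y0)/0.4615 − (y0 − y−2)/2.

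- Variance per woman in units of s²: 2.167² + (2.167 + 0.5)² + 0.5² = 4.69 + 7.11 + 0.25 = 12.06.
- SE of the mean in 12 women: 100 × √12.06 / √12 = 100 mL/year. The on-treatment slope alone has SE 41/0.4615 = 88 mL/year. With five earlier and screening tests, the SE of the difference is 98.
- 95% CI half-width: 2.201 × 100.2 = 221 mL/year. Power to detect full arrest of a decline of 150 mL/year is about 28%, and of 50 mL/year about 7%.

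The comparison is unbiased when all women with earlier tests are used and the untreated course is linear, but it is imprecise.

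**6. Why not restrict to women who were declining.** The screening value enters both the prior slope and the 24-week change, with opposite effect. Suppose the drug is inert, the true decline is 25 mL/year and s = 100.

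- SD of the prior slope: 100/√2 = 70.7 mL/year.
- Selecting slopes below zero: 25/70.7 = 0.354, and the selected mean moves by 70.7 × 0.375/0.638 = 41.5, from −25 to −66.5 mL/year.
- Covariance of change with slope is −s²/2 and the slope variance is s²/2, so the regression coefficient is −1. The selected mean change is −11.5 + 41.5 = +30 mL, against a true −12.
- Spurious paired gain: 30/0.4615 + 66.5 = about 131 mL/year.

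For true declines of 0 and 50 mL/year the spurious gain is about 179 and 92 mL/year. Simulation agrees.

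**The case against.** **Selection is not shown.** A reader might infer that the entry criteria pick women on the slow part of the disease course, so that selection explains any stability. The documents do not support this. The criteria limit the level of lung function and rapalog use, not the rate of fall, and a woman just above the 70% floor may be declining quickly. No decline rate is given. This objection stands: selection is at most a possible contributor, and the missing control and small sample would produce apparent stability without it.

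**The protocol does not claim that stability proves benefit.** This is true. It describes a phase I pilot, sizes the study on adverse events, sets no go rule, and also looks at angiomyolipoma size, VEGF-D and the SGRQ. This limits the severity. It does not remove the point: stabilisation is a named hope, the endpoint is tested at two-sided 0.05, and nothing says how a null result will be read.

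**The added data would be too imprecise to help.** On the assumed figures, the interval for the slope difference is wider than the largest decline considered. That stands as a limit on what the data can show. The value lies in displaying the missing reference rate and the uncertainty around it.

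**Earlier tests are not already being collected.** A reader might take the medical-record review in section V as covering them. It is confined to hospitalisation and side effects, and section III-b mentions past studies only as a source of subjects. Retrieval would be new data collection.

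**Conclusion.** The point holds as a limit on interpretation. With one arm, two lung-function time points and no reference rate, the stated analysis cannot distinguish drug-induced stability from slow untreated disease. The absent control is the main cause. The entry restrictions may add to it, but it would go too far to say that stability would be the product of selection, because the documents contain no rate against which to judge that.

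The size depends on assumed decline rates and SDs. Over the ranges used, an untreated group of 12 would most often show no significant change (about 62% to 95% of trials). The slope calculations further assume equal noise at every test, earlier tests available for all 12 women, and no variation between women in the true change of slope. Real precision would be worse.

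The point concerns stability. A clear improvement would be harder to put down to slow disease, though still uncontrolled. The pilot and safety purpose makes this an inexpensive improvement worth making, not a flaw in the trial's main safety objective.

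**What to change.** 1. In section VI-b, add any existing FEV1, FVC and DLCO results from the 24 months before enrolment as a new data item.
2. In section VI-c, report each woman's pre-treatment slope beside her 24-week change. Give the mean paired difference with a 95% CI in all women who have earlier tests, labelled descriptive, with the number who lack them.
3. Do not restrict this comparison, or any statement about stabilisation, to women with an observed prior decline. Regression to the mean would create a false benefit. Choosing women on pre-screening tests alone would remove the artefact in the 24-week change, but the selected prior slopes would still be exaggerated and the paired difference still biased.
4. In section VI-c, state that no change, or a non-significant Wilcoxon test, will not by itself be read as evidence of benefit.

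The cost is record retrieval for at most 12 women and a short analysis paragraph, with no new visit or test. Some women will have no earlier results, and tests from other laboratories will be noisier. The interval will be wide, and the comparison remains an uncontrolled before-after one. Item 4 is one sentence and is useful even if the records prove sparse.

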Subjects will be provided with written, detailed instruction for calling the study coordinator or physician, including but not limited to infections requiring antibiotics, planned or emergent procedures, or addition of drugs known to interact with Celecoxib. The risk associated with Celecoxib will be explained to the subject in detail. A plan for dose interruption and reduction is included in the experimental plan. Subjects may withdraw from the trial at any time, or be withdrawn by the site PI for safety reasons at his/her discretion. The Data and Safety Monitor will review routine adverse events and trial results every six months, and serious adverse events within 72 hours. [name] will review urgent, persistent or life-threatening adverse events at all times during the trial. An on-call clinician at each site will be available for questions and consultation.

Due to the experimental use of celecoxib in LAM and TSC the trial has been designed with a focus on protecting subjects against risk from the medication including:

- 1- Small sample size consistent with the exploratory nature of the trial.
- 2- Specific exclusion criteria to prevent enrollment of subjects with significant co-morbidities that might place them at excess risk (see exclusion criteria)
- 3- Specific defined dose and holding criteria related to study adverse events.

VIII- Potential benefits

Participation in the proposed research will not guarantee direct benefit to participants, although it remains possible that a previously undiagnosed clinical abnormality will be brought to the clinician's attention. Information obtained from this research will provide information about the relationship between LAM treatment and patient outcomes. Sporadic LAM and Tuberous sclerosis affect more than 1.5 million people worldwide. Lung manifestations of TSC, including LAM are its most life threatening manifestations. Participants may also benefit from the effects of the drug in the trial, as well as frequent follow-up and monitoring. Information learned from this research may benefit women with LAM in the future. Understanding the interplay between mTOR dysregulation and COX 2 inhibition may have implications for patients suffering from other diseases as well.

IX-Data management

Data management overview

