Access to all subject data and information at the clinical sites, including biological samples, will be restricted to authorized personnel. Only authorized personnel at the coordinating center will have access to study data files. Authorized personnel will be assigned user logon IDs, passwords and appropriate access privileges to study data. Study subjects will be identified only by their initials and subject ID number. No personal identifiers such as name, address, social security number will be entered into the study database. Any subject-specific data reported to any study committees will only be identified by subject ID number.

Finally, subjects will not be identified by name in any reports or publications, nor will the data be presented in such a way that the identity of individual subjects can be inferred. Analysis files created for further study by the scientific community will have no subject identifiers.

IX- Monitoring and Quality Assurance

a- Safety Monitoring

We will institute an independent Data Safety Monitoring Board to review procedures and adverse events that occur during the clinical study. Board members will not be involved in the active recruitment and daily routine of the study. The principal investigator will present study progress on a routine basis to the board members. Board members will review new cases and decide whether the study goals should be altered or the study should be stopped.

b- Monitoring of Subjects and Criteria for Withdrawal of Subjects

Subjects will be monitored throughout the clinical trial for new symptoms or complaints.

c- Outcome Monitoring

The clinical outcome of our participants will be continuously monitored by the study staff and the Data Safety Monitoring Board.

d- Adverse event reporting guidelines**Definitions**

Adverse event means any untoward or unfavorable medical occurrence in a human subject, including any abnormal sign (for example, abnormal physical exam or laboratory finding), symptom, or disease, temporally associated with the subject's participation in the research, whether or not considered related to the subject's participation in the research (modified from the definition of adverse events in the 1996 International Conference on Harmonization E-6 Guidelines for Good Clinical Practice).

Serious adverse event means any event temporally associated with the subject's participation in the research that meets any of the following criteria:

- Results in death

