All deaths and all SAEs require reporting from the start of treatment through 28 days after discontinuation of the study. The site is required to call the coordinating center to inform them of the SAE within the 24 hours of knowledge of the event. The site should also submit an SAE form via fax to the coordinating center and enter the SAE information onto the CRF within 24 hours of knowledge of the event.

An updated full written report will be filed as additional information becomes available within 10 working days (14 calendar days). The report will include a complete description of the event, use of all concomitant medications, and the local investigator's assessment of causality of the SAE. Non-serious adverse events will be reported at routine visits, documented on a separate adverse event form, and transmitted to the central coordinating center. All serious and unexpected adverse events will be reported to the overall study PI's.

Expedited Event Reporting

Adverse events that meet the definition of serious, study drug-related and unexpected (per the Investigator's Drug Brochure) qualify for expedited reporting to the regulatory authorities. The DSMB will perform a medical review of all deaths and study drug-related serious adverse events and evaluate for "unexpectedness".

The coordinating center will prepare Med Watch reports for those events identified as serious, study drug-related and unexpected as determined by the DSMB. The coordinating center will submit all unexpected study drug related SAEs as per 21 CFR 32.

Safety events requiring expedite reporting will be sent to the DSMB chair, with forwarding by the chair to the full board as needed, and DOD program office within 1-2 business days. DSMB chair will respond to the overall principal investigator and the coordinating center within 48 hours. Reporting framework and timelines are to be documented in Data and Safety Monitoring Plan after consultation with board members.

Coding for Adverse Events

All reported adverse events will be classified using the Common Terminology Criteria for Adverse Events (CTCAE), version 4.

X- References

Anonymous. (1991). "Lung function testing: selection of reference values and interpretative strategies. American Thoracic Society." Am Rev Respir Dis **144**(5): 1202-1218.

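### Does naming CTCAE v3.0 in one place and version 4 in another leave the grade IV stopping item undefined?

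*Combined protocol and SAP*

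**What the plan says.** Three places in the combined protocol and SAP bear on this.

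- Section V, Primary outcome measurements: "Dose limiting toxicity will be graded according to the National Cancer Institute's CTCAE v3.0", followed by a link to the v3 file. The term dose limiting toxicity appears only here and is not defined.
- Section V, Stopping rules: "The following two types of TRSAEs will be considered for early stopping of the study". The two types are a death related to celecoxib and "Any grade IV toxicity considered to be probably or definitely related to Celecoxib". No version of the scale is given.
- Monitoring and Quality Assurance, part d, Coding for Adverse Events: "All reported adverse events will be classified using the Common Terminology Criteria for Adverse Events (CTCAE), version 4".

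The CTCAE is named nowhere else, and nothing says which version takes precedence. Both statements are current text.

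**The concern.** The main objective is safety and tolerability, and the trial enrols up to 12 women at two centres. With so few subjects, a single related grade IV event could put the study up for early stopping, so whether an event is grade IV matters. The stopping item needs a grade, and the document names two editions of the grading scale. The v3.0 sentence covers only dose limiting toxicity, a term that the stopping item does not use. The version 4 sentence covers all reported adverse events, and a grade IV toxicity is one of those. On that view each site could follow a different sentence and still comply. The same event might then be labelled differently at the two sites, and the reported grades might mix two scales.

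**Working it through.** The concern rests on no sample size, power or alpha figure, so the check is mainly a comparison of passages. It asks where a grade is used and what would change if the version changed.

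**1. Do the two sentences conflict?** The first says that toxicity is graded by v3.0. The second stands under a heading about coding, says that events are classified by version 4, and does not mention grade. The Stopping rules follow the v3.0 sentence within Section V and share its grading language. Reading v3.0 as the grading scale and version 4 as the coding dictionary satisfies every sentence. This is an inference, but nothing in the text contradicts it.

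**2. What does the grade IV label do?** The Stopping rules give no event count, threshold or mandatory halt. The listed events are to be considered. Three other provisions govern review, and none mentions a grade:

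- Section VII, Protection against subject risks related to the study medication: "The Data and Safety Monitor will review routine adverse events and trial results every six months, and serious adverse events within 72 hours".
- Monitoring and Quality Assurance, part a: board members review new cases and "decide whether the study goals should be altered or the study should be stopped".
- Part d, Expedited Event Reporting: "The DSMB will perform a medical review of all deaths and study drug-related serious adverse events".

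The six criteria for a serious adverse event in part d are death, threat to life, hospitalisation, disability, birth defect, and a medical-judgement item. None refers to a CTCAE grade. The count of serious events, and their review, are therefore the same under either version.

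**3. Does a grade enter elsewhere?** Dose adjustment and withdrawal (Section VII, dose interruption, modification or discontinuation) depend on related adverse events and persisting symptoms, with no grade. The tests in Section VI-c concern lung function, angiomyolipoma size and exploratory endpoints. The only safety calculation is Table 2, the probability of at least one event among 12 subjects, 1 − (1 − p)^12:

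- p = 6%: 1 − 0.94^12 = 52.4% (stated 52%)
- p = 2.5%: 1 − 0.975^12 = 26.2% (stated 26%)
- p = 0.2%: 1 − 0.998^12 = 2.37% (stated 2.3%)

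The table reproduces to within rounding or truncation. It is driven by event rates and takes no grade as input.

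**4. Would any event change grade?** The documents contain neither version of the scale, so they cannot show that any event would be graded differently.

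**The case for a change.** The strongest reply is that the division between grading and coding is inferred. All reported adverse events includes grade IV toxicities, and classified need not mean terms only. The link to the v3 file makes a slip in the version number less likely. The Data and Safety Monitoring Plan does not clearly settle the matter, because what is deferred to it is the reporting framework and timelines. Section VI-b also plans to collect the incidence of severe adverse events without a severity scale, although serious may be what was meant.

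There is a further point. The stopping items are introduced as types of treatment related serious adverse event. If that means the event must also meet the seriousness criteria, it is reviewed quickly whatever its grade. If instead a related grade IV toxicity counts as such an event by designation, an event that is not otherwise serious would enter the stopping list through its grade alone. The version could then decide whether it is listed. Without the label it might wait for the six-monthly review of routine events, unless the board saw it sooner as a new case.

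The textual part of this stands: no sentence assigns a version to the stopping item. What does not follow is a consequence. The wider reading matters only for an event that the two versions grade differently, that is probably or definitely related, and that meets none of the six criteria, including the medical-judgement item. The documents point to no such event. They also give no sign that the two sites would grade differently.

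**Conclusion.** The observation is accurate, but it does not call for a change to the plan. It is a small inconsistency in wording with a workable reading: v3.0 for toxicity grades, including the grade IV item, and version 4 for classifying events. Those running the trial can apply that reading, and the report can state the version used. Followed as written, the plan gives the same serious-event counts, the same board review, the same dose-adjustment rule and the same statistical tests under either version. The only thing left open is a label that informs a judgement by a board already free to stop the study.

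This rests on two assumptions: that coding is kept distinct from grading, as the heading suggests, and that the two sites use the same version. If either failed, the effect would still be confined to events graded differently under the two versions. The documents do not show how many there would be, or that there would be any. Asking the sponsor to name a version would tidy the text but brings no demonstrated gain in the safety conclusion.
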